7.2.15. Echocardiogram

An echocardiogram will be obtained at Screening (Visit 1), Week 60 (Visit 7), Week 108 (Visit 11), Week 156 (Visit 15) and Week 216 (Visit 20). In addition, an echocardiogram will be

obtained at the Post-Treatment Visit (6 weeks post discontinuation of ataluren) in patients who discontinue the study after 240 weeks of treatment.

7.2.16. 6-Minute Walk Test

6MWD will be assessed in those patients who are ambulatory (able to run/walk 10 meters in ≤30 seconds) at study entry, using standardized procedures [McDonald 2010] (see Study Manual). The 6MWT will be performed at Screening (Visit 1), Week 24 (Visit 4), Week 48 (Visit 6), Week 72 (Visit 8), Week 96 (Visit 10), Week 120 (Visit 12), Week 144 (Visit 14), Week 168 (Visit 16), Week 192 (Visit 18), Week 216 (Visit 20) and Week 240 (Visit 22 End-of-Treatment/Premature Discontinuation).

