7.2.17. Timed Function Tests

Timed function tests will performed in those patients who are ambulatory at study entry, and include the time taken to stand from supine and time taken to run/walk 10 meters [Mendell 1989, Griggs 1991, Beenakker 2005a, Pradhan 2006] (see Study Manual). These parameters will be monitored at Screening (Visit 1), Week 48 (Visit 6), Week 96 (Visit 10), Week 144 (Visit 14), Week 192 (Visit 18) and Week 240 (Visit 22 End-of-Treatment/Premature Discontinuation).

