1 OVERVIEW

This statistical analysis plan (SAP) details the statistical methods to be used in the analyses and presentation of the data collected in Study PTC124-GD-019-DMD, also referred to as Study 019. Preparation of this SAP incorporates statistical design elements present in the protocol Version 5.0 (dated 18 November 2015). Details are documented in Sections 1-7.

In addition to the protocol defined analyses, a natural history control using the Cooperative International Neuromuscular Research Group (CINRG) will be utilized in order to help to better understand the long-term ataluren data. The planned analysis will be presented in Section 8.

After the implement of protocol Version 5.0, the sponsor has developed the protocol Version 6.1 (dated 08 March 2017) specifically for Canadian sites only for ethics approval when they finished all visits per Version 5.0 and were waiting to roll into another open-label nmDMD Study PTC124-GD-016-DMD conducted in the United States (US). The maximal scheduled visit in Version 5.0 was extended from week 240 to week 336 in Version 6.1. All data collected based on both Versions will be summarized together.

Where conflicts exist between this SAP and the study protocols, the information contained in this SAP supersedes the protocol.

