5.8 Secondary Variables

Subject [REDACTED] will be excluded from the As-Treated population in the analyses of all secondary endpoints.

5.8.1 6-Minute Walk Test

The distance walked at each visit and the change from baseline at each post baseline visit, as obtained from the 6-minute walk test (6MWT), will be summarized descriptively for ambulatory subjects with non-missing baseline 6MWT assessments. The distance walked at each will also be summarized for each actual age.

The endpoint will also be analyzed by means of a mixed model repeated measures (MMRM). An unstructured variance-covariance will be assumed and the estimation method will be the default, ReML. The model will include the factors for treatment, visit, age (6-11, 12-17, and ≥ 18 years), use of corticosteroids at baseline (yes vs no), and baseline 6MWD category (< 300 meters, ≥ 300 - < 400 meters, ≥ 400 meters), and baseline 6MWD as a covariate. Visit is considered as a categorical variable. From this analysis the mean change at each visit will be evaluated. If the model cannot converge, compound symmetry variance-covariance structure will be assumed.

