5.8.2 Timed Function Tests

Timed function test data (ie, time to stand from supine and time to run/walk 10 meters) and change from baseline to each post baseline visit will be summarized descriptively by visit for ambulatory subjects with non-missing baseline timed function tests assessments. Similarly the time to stand from supine and time to run/walk 10 meters will also be summarized for each actual age.

Timed function test (TFT) data imputation rules as the following will be used in the summary.

- If time to run/walk 10 meters > 30 sec, then set to 30 sec.
- If time to stand from supine > 30 sec, then set to 30 sec.

Similar to 6MWT, the time to stand from supine and time to run/walk 10 meters of will also be analyzed by means of a mixed model repeated measures (MMRM) where baseline is baseline time taken to stand from supine and time taken to run/walk 10 meters, respectively.

The Kaplan-Meier method will be applied to the analysis of age at loss of ambulation. The median age at loss of ambulation will be reported by corticosteroids use at baseline. The Kaplan-Meier curves will also be displayed. The age at loss of ambulation is defined as age of the disease progression reported as the adverse event or age at the time to run/walk 10 meters > 30 seconds, whichever occurs earlier. The subjects who are ambulatory at the end of study or discontinuation will be censored on the last valid timed function tests assessment date. Age on that date will be used in the analysis. A sensitivity analysis will be performing based on the loss of ambulation defined only by disease progression AE.

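### If the unstructured MMRM fails to converge, the only fallback is compound symmetry, which would understate late-visit and overstate early-visit uncertainty to the extent that the variance of change grows over time.

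*SAP*

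**What the plan says.** For 6-minute walk distance (6MWD), SAP 5.8.1 states: "An unstructured variance-covariance will be assumed and the estimation method will be the default, ReML". Visit is categorical and the output is by visit: "From this analysis the mean change at each visit will be evaluated". The single contingency is: "If the model cannot converge, compound symmetry variance-covariance structure will be assumed". Neither document mentions an intermediate structure, a structure with visit-specific variances, or a robust standard error for this model.

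SAP 5.8.2 carries the approach to the timed function tests, which "will also be analyzed by means of a mixed model repeated measures (MMRM) where baseline is baseline time taken to stand from supine" (and likewise for the 10-metre run/walk).

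Three other provisions matter here:

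- **Schedule.** Protocol 7.2.16 places the walk test every 24 weeks, and Protocol 7.2.17 places the timed tests every 48 weeks, both ending at Week 240.
- **Later and off-schedule data.** SAP 1 reports, for Canadian sites, that "The maximal scheduled visit in Version 5.0 was extended from week 240 to week 336 in Version 6.1", and pools all data. SAP 6.1 maps early-termination and unscheduled visits into 12-week windows.
- **Descriptive summaries.** SAP 5.1 requires n, SD, SE and a 95% CI in every summary of a continuous variable.

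**The concern.** An unstructured matrix lets each visit have its own variance. Compound symmetry forces one variance on all visits and one correlation on all pairs of visits. If boys decline at different rates, the variance of change from baseline rises with follow-up. A pooled variance is then too large for the first visits and too small for the last. Because the MMRM is used to read off the mean change at each visit, the error falls on exactly the quantity reported. It flatters the precision of the long-term estimates.

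The step in the SAP is abrupt. It goes from the most flexible structure to one of the most restrictive, although structures between the two keep visit-specific variances and need far fewer parameters.

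**Working it through.** The plan states no figure to reproduce: there is no formal hypothesis (SAP 3.4), and no SD or interval width is given for the MMRM.

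**1. Number of covariance parameters.** With k post-baseline visits, an unstructured matrix has k(k+1)/2 parameters.

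- 6MWD to Week 240: k = 10, so 10 × 11/2 = 55.
- Timed tests to Week 240: k = 5, so 5 × 6/2 = 15.
- To Week 336, assuming that the 24- and 48-week intervals continue (the documents do not say): k = 14 gives 105, and k = 7 gives 28.
- If every window listed in SAP 6.1 held a test: k = 27 gives 27 × 28/2 = 378.

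The data come from the ambulatory part of up to about 96 boys. The ambulatory number is not given.

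**2. Would the unstructured model fail?** A parameter count does not settle this, so unstructured REML was fitted to simulated data with 10 scheduled visits (assumed slope SD 30 m/year, test SD 25 m, six covariate terms). With 50 boys and 4% dropout per visit, about 34 boys remained at the last visit and 60 of 60 fits converged to a positive-definite matrix. With 40 boys and 6% dropout per visit, about 23 remained and again 60 of 60 converged.

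The realistic trigger is sparse windows. Protocol 7.2.1.3 has boys who leave early repeat the Week 240 procedures (if their last visit was more than 3 weeks before). SAP 6.1 then assigns those tests to the nearest 12-week window, and SAP 5.8.1 does not limit the MMRM to scheduled visits. If, say, the Week 60 window holds walk tests only from boys who then left, no boy informs the covariance of Week 60 with any later visit, and that parameter cannot be estimated. Windows after Week 240, filled by Canadian sites only, may be similarly thin.

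**3. Size of the error if the fallback is used.** With complete data, compound symmetry replaces each visit's variance by the average over visits. The ratio of interval width to correct width at visit t is √(mean of SD² over visits)/SD_t. The coverage of a nominal 95% interval is 2Φ(1.96 × ratio) − 1.

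Assume that the SD rises linearly from 1 at the first visit to g at the last, over 10 visits. For g = 2 the mean variance is 2.352, with square root 1.53. The first-visit ratio is then 1.53/1 = 1.53, the last-visit ratio 1.53/2 = 0.77, and last-visit coverage 2Φ(1.50) − 1 = 0.87.

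| SD growth g (assumed) | First-visit ratio | Last-visit ratio | Last-visit coverage |
|---|---|---|---|
| 1 | 1.00 | 1.00 | 95% |
| 1.25 | 1.13 | 0.90 | 92% |
| 1.5 | 1.26 | 0.84 | 90% |
| 2 | 1.53 | 0.77 | 87% |
| 3 | 2.10 | 0.70 | 83% |
| 4 | 2.68 | 0.67 | 81% |

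For five visits (timed tests), g from 1.5 to 3 gives first-visit ratios of 1.26 to 2.12 and last-visit ratios of 0.84 to 0.71.

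**4. Check by simulation.** Compound-symmetry REML fits to random-slope data (48 or 80 boys; dropout 0 or 10% per year; slope SD 10, 20 or 40 m/year; SD growth 1.36 to 3.59; all assumed) gave first-visit SE ratios of 1.06 to 2.41. Last-visit ratios were 0.85 to 0.59, with last-visit coverage of 90% to 75%. The direction was the same in every run, and the late-visit shortfall was somewhat larger than in the table because variance under random slopes is concentrated at the end.

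**5. Check of the remedy.** In the same fits, sandwich standard errors gave SE ratios of 0.92 to 1.07 at the first visit and 0.94 to 1.02 at the last, with coverage of 92% to 96% at both.

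**The case against.** The strongest reply is that this is a contingency clause in a supportive analysis.

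- **The fallback may never be used.** This stands for the scheduled visits: in the trial fits above, 55 parameters did not stop the model converging. A reader might infer from the parameter count that the fallback is likely. The documents do not support that; they make it plausible only through sparse windows, whose occupancy they do not report.
- **The size is assumed.** This also stands. No by-visit SD appears anywhere. A reader might infer that late intervals would be far too narrow, but that needs SD growth of about threefold or more. At 1.25-fold the loss is about 10%. Walk distance cannot fall below zero, which limits the growth.
- **Little rests on the model.** The primary endpoint is safety, and 6MWD is secondary with no formal hypothesis. The planned natural-history comparisons in SAP 8.2.1 use Kaplan-Meier methods, log-rank tests and piece-wise regression of FVC. The descriptive 95% CIs from SAP 5.1 use each visit's own SD and would sit beside the MMRM results. So the documents do not support reading this as a threat to the study's main conclusion.
- **The timed tests are less exposed.** This stands for the schedule: five visits to Week 240, and a 30-second cap that limits variance growth.

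What survives is the rule itself. If the clause is invoked and the variance grows, the error has a known direction and nothing in the SAP corrects it. The descriptive intervals do not replace the model, because they describe only the boys still observed at each visit.

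**Conclusion.** The point holds as a conditional one. Given non-convergence and growing variance of change, the specified fallback misstates by-visit uncertainty. Under assumed SD growth of 1.25, 2 and 3 to 4, last-visit intervals are about 10%, 23% and 30 to 33% too narrow, and first-visit intervals are about 1.1, 1.5 and 2.1 to 2.7 times as wide as they should be. With constant variance across visits there is no error.

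The direction rests on boys declining at different rates, which is plausible in a disease that Protocol 2.1 describes as progressive. The size rests wholly on the assumed SD growth. It would go too far to say that the plan as written produces wrong error bars: the primary specification is unstructured, and the problem lies only in its contingency.

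**What to change.** In SAP 5.8.1, and by reference in 5.8.2, replace the compound-symmetry fallback with a pre-specified sequence of structures that allow visit-specific variances. One example is heterogeneous Toeplitz, then heterogeneous AR(1) or heterogeneous compound symmetry; the exact order matters less than fixing it in advance. State that empirical (sandwich) standard errors will be used for any structure other than unstructured. The two parts do different work: sandwich errors repair the intervals, but they do not correct any effect of a poor covariance structure on the estimated means when dropout depends on earlier decline.

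Optionally, fit the MMRM to scheduled visits through Week 240 and show later and off-schedule visits descriptively. This removes the most plausible cause of non-convergence, but it changes the pooling of all data stated in SAP 1 and is a separate choice.

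The cost is a few sentences in the SAP and a few lines of code. If a fallback is needed, late-visit intervals will be wider than under compound symmetry. Label: cheap improvement.

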5.8.2 Timed Function Tests

Timed function test data (ie, time to stand from supine and time to run/walk 10 meters) and change from baseline to each post baseline visit will be summarized descriptively by visit for ambulatory subjects with non-missing baseline timed function tests assessments. Similarly the time to stand from supine and time to run/walk 10 meters will also be summarized for each actual age.

Timed function test (TFT) data imputation rules as the following will be used in the summary.

- If time to run/walk 10 meters > 30 sec, then set to 30 sec.
- If time to stand from supine > 30 sec, then set to 30 sec.

Similar to 6MWT, the time to stand from supine and time to run/walk 10 meters of will also be analyzed by means of a mixed model repeated measures (MMRM) where baseline is baseline time taken to stand from supine and time taken to run/walk 10 meters, respectively.

The Kaplan-Meier method will be applied to the analysis of age at loss of ambulation. The median age at loss of ambulation will be reported by corticosteroids use at baseline. The Kaplan-Meier curves will also be displayed. The age at loss of ambulation is defined as age of the disease progression reported as the adverse event or age at the time to run/walk 10 meters > 30 seconds, whichever occurs earlier. The subjects who are ambulatory at the end of study or discontinuation will be censored on the last valid timed function tests assessment date. Age on that date will be used in the analysis. A sensitivity analysis will be performing based on the loss of ambulation defined only by disease progression AE.

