5.8.3 North Star Ambulatory Assessment

The NSAA consists of 17 activities, each scored as 0, 1, or 2. The sum of these 17 scores will be used to form a total score. If fewer than 13 of the 17 activities are performed, the total score will be considered missing. If from 13 to 16 activities are performed, the total score will be calculated by multiplying the sum of the scores in the x activities that were performed by $17/x$. If an activity cannot be performed due to disease progression/loss of ambulation, a score of zero will be assigned. The linear score is the linear transformation of the NSAA score to a scale of 0 to 100 [Mayhew 2013].

Total scores and linear scores from the North Star Ambulatory Assessment will be summarized by visit and change from baseline to each post baseline visit will be summarized descriptively for ambulatory subjects with non-missing baseline NSAA assessments. Similarly the total and linear scores will also be summarized for each actual age.

The number and proportion of loss of function of each North Star Ambulatory Assessment item at week 48 will be tabulated. The function loss defined as a shift from non-zero at baseline to zero at week 48. The missing data will be handled by last observation carried forward (LOCF).

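### SAP 5.8.1 and 5.8.2 do not say what value a 6MWT or stand-from-supine test takes when disease prevents it, so late means may describe only the boys still able

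*SAP*

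**What the plan says.** **6MWT (SAP 5.8.1).** Distance and change from baseline "will be summarized descriptively for ambulatory subjects with non-missing baseline 6MWT assessments". A by-age table follows: "The distance walked at each will also be summarized for each actual age". An MMRM with unstructured covariance is added, with a fallback: "If the model cannot converge, compound symmetry variance-covariance structure will be assumed". No value is given for a walk that disease prevents.

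**Timed tests (SAP 5.8.2).** The rules are introduced by "Timed function test (TFT) data imputation rules as the following will be used in the summary". The rule for rising is "If time to stand from supine > 30 sec, then set to 30 sec", and the 10-m run/walk has the same cap. Neither rule names a test that was not completed, and the text does not say whether the cap also enters the MMRM. By-age tables are planned here too: "Similarly the time to stand from supine and time to run/walk 10 meters will also be summarized for each actual age".

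**NSAA (SAP 5.8.3).** Here inability is handled: "If an activity cannot be performed due to disease progression/loss of ambulation, a score of zero will be assigned".

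**Who is tested (Protocol 7.2.16 and 7.2.17).** Both test sets are fixed by ambulatory status at study entry. Both sections refer to the Study Manual for procedures.

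**CINRG (SAP 8.2.1).** By-age summaries of the same tests are planned for the natural-history data. Only the NSAA scoring is expressly carried over to it.

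**The concern.** A boy who walks at entry and later cannot walk stays in the 6MWT and timed-test sets. If his later tests are simply blank, he leaves the mean at the point where he has declined most. The late means then come from the boys who kept the ability, and the cohort looks better preserved than it is.

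The plan meets this problem for NSAA and not for the other two kinds of functional measure. NSAA items include rising from the floor (Protocol 13.2.6.3), and NSAA and the timed tests share the 48-week visits. A boy who cannot rise therefore has a defined NSAA score and, at the same visit, no clearly defined stand-from-supine time. A boy who walks but cannot rise at screening is also affected. He either drops out under the non-missing-baseline condition or enters at 30 s, depending on coding that the SAP does not state.

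SAP 8.1 wants the CINRG data to inform long-term benefit. If inability were coded differently in the two sources, their by-age tables could differ for that reason alone.

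**Working it through.** The plan has no figure of its own to reproduce: SAP 3.4 states that there is no formal hypothesis.

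**1. The rules side by side**

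| Measure | Stated handling when disease prevents the test |
|---|---|
| NSAA item | Scored 0 (SAP 5.8.3) |
| 10-m run/walk | Time over 30 s becomes 30 s. Inability is not named, but Protocol 3.2 and SAP 3.2 define nonambulatory as not managing 10 m within 30 s, so it can be read as over 30 s |
| Stand from supine | Time over 30 s becomes 30 s. Inability is not named and no definition links it to the cap |
| 6MWD | None |

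No other section closes the gap. Protocol 10.4.6.1 uses the best valid test and lists invalid ones. SAP 6 covers visit windows, baseline, change and missing dates. LOCF appears only with the Week 48 NSAA item table.

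**2. Is inability to be expected?** 240 weeks is 240 × 7 / 365.25 = 4.6 years. The Version 6.1 extension to Week 336 (SAP 1) is 6.4 years. Protocol 2.1 says that most boys have trouble rising by age 8 and that most depend on a wheelchair by 10 to 14. Matched ambulatory entrants are aged 9–18 (SAP 8.2). Inability is therefore expected during follow-up, but no loss rate is given.

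**3. By-age mean distance.** Let M be the mean in boys able to walk and p the share unable.
- Mean with inability at 0 m = (1 − p) × M.
- Relative excess of the able-only mean = M / [(1 − p)M] − 1 = p/(1 − p).
- p = 5%: 0.05/0.95 = 5%. p = 10%: 0.10/0.90 = 11%. p = 20%: 0.20/0.80 = 25%.
- Example with an assumed M of 300 m and p = 20%: 0.8 × 300 = 240 m, and 300/240 = 1.25.

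**4. By-visit change in distance.** Let D be the walkers' mean decline and B the mean baseline of the boys who lost the ability.
- Able-only change = −D.
- Change with 0 m scoring = −(1 − p)D − pB.
- Gap = p × (B − D).

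The able-only figure understates decline whenever B exceeds D. The gap vanishes as p approaches 0, so early visits are little affected. Boys who lose walking may have started lower, so the percentages in step 3 do not carry over to change scores.

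**5. Stand from supine, if inability is left missing.** Mean with inability at 30 s = (1 − p) × M + 30p. With an assumed M of 8 s:
- p = 10%: 7.2 + 3.0 = 10.2 s.
- p = 20%: 6.4 + 6.0 = 12.4 s.

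If inability already enters as 30 s, there is no gap.

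**6. MMRM.** With blanks after loss, the model treats those visits as missing at random and estimates a walking distance that the boy no longer has. It can project a steep decline for boys who were falling before they stopped. The direction against 0 m scoring is therefore not fixed.

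**7. A separate conflict.** The EK row of the SAP 8.2 matching table requires ambulatory status at entry, with a baseline score of 0–15. Protocol 3.3, Protocol 7.2.19 and SAP 3.3 define and schedule EK for nonambulatory patients.

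**The case against.** The strongest reply is that the Study Manual may already code inability. It governs both tests and is not available here. This stands as a condition on the whole point: the documents show that the SAP neither states nor cites a code, not that the data lack one.

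For stand from supine there is also internal evidence of a code. SAP 5.8.2 calls its rules imputation, an odd word for trimming a recorded time. The matched baseline range in SAP 8.2 runs from 2.3 to exactly 30 s, while the 10-m range stops at 26.4 s. That fits non-risers entering at 30 s. A reader might infer that the plan has no value at all for a boy who cannot rise. The documents do not support that; the wording is ambiguous. For 6MWD there is no such reading, because there is no cap.

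Zero is a natural floor for a 0–2 item, whereas 0 m or 30 s turns a continuous measure into a composite. Observed-only summaries are a legitimate description. This is why the scored versions should be added and the observed ones kept.

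Finally, these are secondary endpoints in a single-arm safety study. Each summary shows n, and SAP 8.2.1 lists no formal CINRG test for 6MWD or the timed tests. Loss of ambulation has its own Kaplan-Meier analysis. All of this limits the stakes. However, n does not separate inability from dropout, and the Kaplan-Meier event ("The age at loss of ambulation is defined as age of the disease progression reported as the adverse event", or a 10-m time over 30 s if earlier) does not register inability to rise and leaves the means unchanged.

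**Conclusion.** The gap is real for 6MWD, and the wording is ambiguous for stand from supine. Unless the Study Manual codes inability, the late by-visit and by-age 6MWD means describe only boys still able and understate the cohort's decline. The stand-from-supine means do the same if inability is left missing.

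The size cannot be determined. The excess of p/(1 − p), 11% at p = 10% and 25% at p = 20%, is exact for by-age mean distance, but p is assumed and 0 m is the chosen score for inability.

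Two stronger conclusions might be inferred and are not supported. One is that the planned unstructured MMRM understates decline: its direction depends on the boys' trajectories, and the documents do not show it. The other is that the CINRG by-age tables favour ataluren: the documents leave the coding open in both sources and so imply no direction.

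This is a worthwhile, inexpensive improvement to secondary descriptive analyses. It does not touch the primary safety objective. The EK row is a separate inconsistency to reconcile.

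**What to change.** **SAP 5.8.1 and 5.8.2**
- Keep the observed-only summaries.
- Add by-visit and by-age summaries with 6MWD = 0 m, and stand from supine and 10-m run/walk = 30 s, when the test cannot be done because of disease. Decide test by test: a boy who walks but cannot rise gets 30 s for rising only.
- Report at each visit the number unable because of disease and, separately, the number missing for other reasons.
- Run the MMRM with and without these values and the 30 s cap, as a sensitivity analysis.

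**SAP 8.2.1.** Apply the same rules to the CINRG by-age summaries, as is already done for NSAA.

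If the Study Manual already codes inability, cite it and use the same code for CINRG.

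**SAP 8.2.** Reconcile the EK row with Protocol 3.3, Protocol 7.2.19 and SAP 3.3.

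**Cost.** SAP wording, one extra set of descriptive tables and a repeat model run; no change to visits or treatment. The NSAA rule already requires the reason for inability at the 48-week visits. The 6MWT visits at Weeks 24, 72, 120, 168 and 216 have no scheduled NSAA, and the reason may not be captured there. Recorded loss of ambulation can stand in, but may miss a boy who stops the 6MWT earlier. The scored endpoint mixes ability with performance and is less normal, which is a further reason to show both versions.
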